3 NON-UW RESEARCH SETTING

Complete this section only if your research will take place outside of UW and Harborview

3.1 Reason for sites. Describe the reason(s) why you selected the sites where you will conduct the research.

We will still operate the study out of Gay City and Kelley-Ross pharmacy, and the reasons for selecting those sites are below. At this time we propose to broaden study sites to any provider or organization in King County who provides PrEP to someone who is eligible (for example, Madison Clinic at Harborview, Public Health King County STD clinic, private practitioners) and contacts us if the person is interested in participating. During the

first few months of this study we have seen a very small number of eligible people at Gay City and Kelley-Ross (recent methamphetamine use and seeking PrEP). We have brainstormed and asked community partners regarding approaches to broaden our reach to engage with more individuals who may be eligible and interested to enroll in the study. We have provided study information to colleagues and community partners and believe that some may have persons who seek PrEP from them and would be interested in participating in this study. Furthermore, aside from the consent process and fingerstick dried blood spot collection all research procedures (e.g., peer navigation, surveys) are done outside of the study site.

We selected two non-UW sites to participate in this study: Gay City and Kelley-Ross. These sites were selected for several reasons. First, both Gay City and Kelley-Ross have dedicated PrEP clinics, where meth-using MSM/TG (the target population) seek PrEP. Second, the UW research team has existing relationships with both clinic's leadership, and the PI, [name], is the Medical Director and PrEP provider at Gay City. Finally, in the surveys we did as part of study #54, we asked meth-using MSM/TG where they would like to access PrEP and both Gay City and Kelley-Ross were in the top half in both surveys with 33% saying they would like to get PrEP at Gay City and 27% saying Kelley-Ross in our final survey.

3.2 Local context. Culturally-appropriate procedures and an understanding of local context are an important part of protecting subjects. Describe any site-specific cultural issues, customs, beliefs, or values that may affect your research or how it is conducted.

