5 PROCEDURES

5.1 Study procedures. Using lay language, provide a complete description of the study procedures, including the sequence, intervention or manipulation (if any), drug dosing information (if any), use of records, time required, and setting/location. If it is available and you think it would be helpful to the IRB: Upload a study flow sheet or table to the **Supporting Documents** SmartForm in **Zipline**.

For studies comparing standards of care: It is important to accurately identify the research procedures. See UW IRB [POLICY: Risks of Harm from Standard Care](#) and the draft guidance from the federal Office of Human Research Protections, ["Guidance on Disclosing Reasonably Foreseeable Risks in Research Evaluating Standards of Care"](#); October 20, 2014.

This research study will be conducted in addition to standard of care procedures for PrEP use. Therefore, clinical procedures, including blood draws for laboratory testing, STI screening, PrEP prescriptions, and adherence counseling will be performed in accordance with the clinic's standard of care. Participants will be followed in this study and have visits at entry (baseline), and then at months 1, 3 and 6.

The research procedures, in addition to informed consent, that all participants will get in addition to the standard of care, are the following:

- Randomization: After consent has been obtained the clinical site will send documentation of eligibility (checklist) and the signed informed consent, HIPAA authorization, and ROI to the study team at UW. The site will either email the documents or provide them in person to a study team member. Once these documents are received, the research coordinator will send the participant a link to the baseline survey. After completion of the baseline survey, the participant will be randomized to one of the two intervention groups: standard of care, or peer navigation. The research coordinator will open a sequentially numbered, sealed envelope with the study allocation (generated by site using blocked randomization with variable block sizes and random number generator). They will record the treatment assignment of the participant in their de-identified chart and send a text or email to inform the participant of their assignment.

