- Surveys: Participants will be asked to complete an online survey at the entry visit (baseline) and at 3 and 6 months. They will be sent a unique link to the survey by text and reminders if they do not complete it. If a participant does not complete their baseline survey within 7 days they will be replaced in the study. Extenuating circumstances (such as sudden job loss, health emergencies and legal issues for robberies) can be made to extend this baseline survey deadline within a reasonable timeframe at the discretion of the PI.

- Fingerstick for dried blood spots: At all follow-up visits (1 month, 3 months, and 6 months) we will collect a blood specimen via fingerstick and use it to obtain dried blood spots, which will be used to test for the presence of the medications in PrEP (tenofovir and emtricitabine).
- Intervention groups:
 - Standard of care: The up to 20 participants who are assigned to the standard of care, will only be asked to participate in the research procedures described above.
 - Peer navigation: For the up to 20 participants who are assigned to the peer navigation group, they will receive peer support. These activities include, but are not limited to, in-person meetings, appointment reminders and escort, refill assistance, and check-ins about adherence. The activities that the participant receives will be in response to their needs and requests. The peer will introduce themselves to participants in this intervention arm within 2 business days of when the participant completes the survey, via their preferred method of contact (as recorded at the clinic during the entry visit). The peer will schedule their first in-person meeting within 1 week of enrollment. As some meth users will have greater functioning than others, the peer will create an individualized plan for each subject and tailor activities and resources based on acuity. Individualized plans will be completed at study enrollment and exit to be able to record needs and progress during the study. Additional individualized plans may be completed during follow-up at the discretion of the peer and depending on the needs and acuity of the participant.

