If a participant decides to stop getting PrEP at one of our study clinics, and gets PrEP somewhere else during their 6-month study participation, we will ask them to take the remaining online study surveys and to complete an ROI between their new clinic and the study site where they enrolled. If they are in one of the groups that receive text messages or peer navigation, we will also ask that they continue to receive these interventions to try and support their PrEP use at the other provider. If a participant leaves the study early (before 6 months) we will attempt to complete a study exit visit that will have the same procedures as a visit at months 3 or 6 (survey and dried blood spot).

Finally, the research coordinator will conduct semi-structured interviews with all willing study participants after they finish study follow-up to better understand the acceptability and feasibility of the study interventions and participants experience with PrEP. Interviews will be digitally audio-recorded and transcribed verbatim, and identifying information will be deleted. The information sheet and interview guide for these interviews have been uploaded to Zipline. Once a participant completes their final, 6-month survey, or if a participant discontinues the study early, the research coordinator will contact them and ask if they would like to participate in an end-of-study interview. Interviews can be conducted in-person, by phone, or by Zoom videoconference. If the interview is conducted by phone or Zoom the research coordinator will email the information sheet to the participant prior to the interview and will ensure that all questions are answered and verbal consent is obtained at the start of the interview before asking any interview questions. If the interview is done in-person the information sheet will be reviewed at the beginning of the interview and verbal consent will be obtained prior to asking any interview questions. \$40 Amazon gift cards will be provided for each completed interview, which will either be handed to participants or emailed.

Procedures	Enrollment ¹	Month 1	Month 3	Month 6	Early Discontinuation
Clinical Procedures					
HIV Testing	X	X	X	X	X
HBsAg Testing	X				
Creatinine Testing	X	X	X	X	X
STI Screening	X		X	X	X
Adherence Counseling	X	X	X	X	X
Research Procedures					
Research Consent	X				
Online CASI	X		X	X	X
Blood collection for DBS		X	X	X	X
Blood volume (mL)	15	7	15	15	15
Clinic visit length (min)	90	30	30	30	30

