In response to the study sponsor's request we have formed a DSMB for this study. The DSMB will meet prior to the start of the study to review the protocol and annually until study completion. The Data Safety and Monitoring Plan (DSMP) that is uploaded to the Supporting Document SmartForm supersedes the DSMP that was originally proposed in the Funding Application.

10.6 Un-blinding. If this is a double-blinded or single-blinded study in which the participant and/or you do not know the group to which the participant is assigned: describe the circumstances under which un-blinding would be necessary, and to whom the un-blinded information would be provided.

10.7 Withdrawal of participants. If applicable, describe the anticipated circumstances under which participants will be withdrawn from the research without their consent. Also, describe any procedures for orderly withdrawal of a participant, regardless of the reason, including whether it will involve partial withdrawal from procedures and any intervention but continued data collection or long-term follow-up.

While the study team will do their best to retain all participants for the duration of the study, it is possible that participants will discontinue their participation early, before the final 6-month visit. This could occur due to participant choice, study team decision, or experiencing an adverse event (AE). If someone has an AE related to PrEP and is willing to remain in the study, we will discontinue PrEP in that participant, but continue to follow them to monitor the AE and its resolution. If someone exits the study early, we will attempt to schedule a final visit that will include the same procedures as a scheduled month 3 or 6 visit. If a participant refuses to return for a final visit, we will ask them to at least complete an exit CASI. Reasons for early discontinuation will be recorded on study data collection forms.

In addition, the study team will discontinue participants if they do not complete a baseline CASI within 7 days (with the exception of extenuating circumstances) of their entry visit, in which case they will be replaced. If the study team thinks that the participation of a study participant could cause harm to them or the study

staff (e.g., inappropriate, aggressive behavior), the study team may end participation for that participant early. We do not expect this to occur.

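### Do participants who move their PrEP care elsewhere, but stay in the study, drop out of dried blood spot collection?

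*Protocol*

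**What the plan says.** Protocol section 5.1 sets out the research procedures under a general heading: "The research procedures, in addition to informed consent, that all participants will get in addition to the standard of care, are the following". One of the items under it is the fingerstick: "At all follow-up visits (1 month, 3 months, and 6 months) we will collect a blood specimen via fingerstick". The visit table in the same section marks blood collection for DBS at months 1, 3 and 6 and at early discontinuation.

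A later paragraph of 5.1 deals with someone who gets PrEP elsewhere during the 6 months. It gives three things:
- the remaining surveys and a records release: "we will ask them to take the remaining online study surveys and to complete an ROI between their new clinic and the study site";
- for those assigned an intervention, "we will also ask that they continue to receive these interventions to try and support their PrEP use at the other provider";
- in its last sentence, for people who leave the study early, an attempt at an "exit visit that will have the same procedures as a visit at months 3 or 6 (survey and dried blood spot").

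Section 10.7 adds a fallback for people who leave: "If a participant refuses to return for a final visit, we will ask them to at least complete an exit CASI".

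On location, section 3.1 says that "aside from the consent process and fingerstick dried blood spot collection all research procedures" take place away from the study site, and section 9.6 describes the spots as taken at the clinic.

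**The concern.** The transfer paragraph reads like a complete list of what is asked of someone whose PrEP care has moved. It restates the surveys, which are also scheduled for everyone, but not the spots. Its last sentence does name the spots, for people who leave the study. Read literally, leavers are expressly asked for a spot and transferred participants who stay are not.

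The omission falls on a procedure sensitive to a change of clinic. Surveys and peer contact can follow a participant anywhere, whereas the spot needs a visit. Transfer is also foreseeable: section 8.2d describes Gay City as following people only until they are linked to primary care, usually within a few months, which can fall inside the 6-month follow-up.

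Drug levels would be at stake. Tenofovir and emtricitabine results are planned data (section 5.2), and section 1.8 names adherence monitoring as a need. The records release and the refill data, which section 5.3 promises only as available, can show prescribing and dispensing after transfer but not a drug level. If staff took the list as exhaustive, levels would be missing for people still under follow-up, and that loss would depend on linkage to care.

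**Working it through.** The question turns on the text, and the protocol gives no figure to reproduce. The passages come first, then the size if the spots were in fact missed.

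**Step 1. Does any passage remove the spots after transfer?**

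| Place | Who it covers | DBS |
|---|---|---|
| 5.1, general list of research procedures | all participants | months 1, 3 and 6 |
| 5.1, visit table | all participants | months 1, 3 and 6, and early discontinuation |
| 5.1, transfer sentences | PrEP moved, still in study | not mentioned |
| 5.1, last sentence of that paragraph | left the study early | attempted at an exit visit |
| 10.7 | left, and refuses to return | exit survey alone as fallback |

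The general rule has no carve-out for transfer, and the transfer sentences do not say that any procedure stops. Section 5.1 also describes visits at months 1, 3 and 6 as part of being followed in the study, without making them depend on where PrEP is prescribed. People who have left are still asked for a spot, and the survey becomes the sole request only on refusal. It would be odd for the protocol to want spots from leavers but not from people still enrolled. The consistent reading is that the schedule continues.

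**Step 2. Size per person if no later spot is obtained.** The schedule has 3 spots.
- Transfer before month 1: 3 of 3 lost.
- Between months 1 and 3: 2 of 3 lost.
- Between months 3 and 6: 1 of 3 lost.

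With up to 20 per arm (section 2.7), one such person is 1/20 = 5% of a full arm's month-6 spots.

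**Step 3. Size per arm.** Let f be the share of an arm that transfers and q the share of those with no later spot. The expected number of missing month-6 spots in a full arm is 20 × f × q. Neither f nor q is in the protocol; the values below are assumptions.

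| f | q = 0 | q = 0.5 | q = 1 |
|---|---|---|---|
| 10% | 0 | 1 | 2 |
| 25% | 0 | 2.5 | 5 |

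**Step 4. Effect on precision, for scale only.** Take one arm's proportion at 50%, with 95% half-width 1.96 × √(0.25/n). The range that makes no assumption about k missing people is k/20 wide.

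| Missing (k) | n | Half-width, points | No-assumption range, points |
|---|---|---|---|
| 0 | 20 | 21.9 | 0 |
| 1 | 19 | 22.5 | 5 |
| 2 | 18 | 23.1 | 10 |
| 5 | 15 | 25.3 | 25 |

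The protocol does not name this proportion as an endpoint. An arm of 20 is imprecise with or without the loss: 5 missing people add 25.3 − 21.9 = 3.4 points to the half-width. The no-assumption range widens more, to 25 points, but only under the least favourable pair of assumed values.

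**The case for a change.** The strongest case for amending is practical. A coordinator handling a transfer will look at the transfer paragraph, and what it lists may become what is done. The spots sit in the visit table beside clinical tests that follow the clinic's standard of care, and the protocol does not say where the study visit happens once that care has moved. Section 5.11 describes survey links and reminders for everyone but no further contact with the standard of care group until the interview invitation, and section 4.4 lists payment for surveys and interviews but none for spots. So little in the text would prompt a transferred standard of care participant to come back. A missed spot cannot be recovered, and one clause would settle the matter.

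Some of this stands. The omission is noticeable because the surveys are restated, and the place of collection after transfer is left open. But the step from an incomplete sentence to lost spots is conjecture about staff behaviour. Section 12.2 has the investigator, coordinator and peer meeting regularly to review participants' disposition, with the coordinator responsible for seeing that procedures are communicated. The frequency is also unknown: the remark about early linkage concerns Gay City only, and section 3.1 proposes to "broaden study sites to any provider or organization in King County who provides PrEP to someone who is eligible", so a receiving clinic might itself be a study site. The protocol does not settle that.

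**Conclusion.** No change to the plan is needed. The transfer sentences leave out the spots, but the rule for all participants and the visit table still apply, and nothing contradicts or waives them. An added clause would restate a rule already in force. It could tidy the text at the next revision, but no analysis depends on it.

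The size runs from zero, if staff apply the general schedule, to 5 of 20 month-6 spots in an arm under the least favourable assumed values (a quarter of the arm transfers and none of them gives a later spot). The protocol supports neither value, so the actual amount cannot be derived. Spots taken before transfer are kept in any case, and surveys, released records and available refill data continue.

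The conclusion also rests on the role of the drug levels. Section 1.5 states the aim as acceptability and feasibility, and no drug-level endpoint or between-arm comparison of levels is named. Some missing levels would thin the adherence data without undermining the stated aim, and nothing in the text points to bias between arms.

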5.3 Data sources. For all types of data that you will access or collect for this research: Identify whether you are obtaining the data from the subjects (or subjects' specimens) or whether you are obtaining the data from some other source (and identify the source).

If you have already provided this information in Question 5.1, you do not need to repeat the information here.

We are obtaining the data from the subject (contact information, self-reported survey data, dried blood spots, reported behavior and PrEP adherence, etc.). We will also obtain PrEP pharmacy refill data as available. We will also collect data recorded by the peer (individualized plan, contact log), and data recorded on the text platform (number of texts, content, etc.). Correspondence between the peer and the participants assigned to the peer navigation group will also be considered study data. We will count the frequency of contacts of different types (e.g., text, call, in-person) and describe the contact (e.g., call to pharmacy to help with refills).

5.4 Retrospective/prospective. For all types of data and specimens that you will access or collect for this research: do all data and specimens to be used in the research exist (for example, in subjects' medical records) at the time this application is being submitted for initial review?

	No
	Yes

Include any necessary comments or explanation below (Note that for most studies this can be left blank):

5.5 Identifiability of data and specimens. Answer these questions carefully and completely. This will allow HSD to accurately determine the type of review that is required and to assist you in identifying relevant compliance requirements. Review the following definitions before answering the questions:

Access means to view or perceive data, but not to possess or record it. See, in contrast, the definition of "obtain".

Identifiable means that the identity of an individual is or may be readily (1) ascertained by the researcher or any other member of the study team from specific data variables or from a combination of data variables, or (2) associated with the information.

Direct identifiers are direct links between a subject and data/specimens. Examples include (but are not limited to): name, date of birth, medical record number, email or IP address, pathology or surgery accession number, student number, or a collection of your data that is (when taken together) identifiable.

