PHI is individually-identifiable healthcare record information or clinical specimens from an organization considered a "covered entity" by federal HIPAA regulations, in any form or media, whether electronic, paper, or oral. If you will use UW Medical Records, you must answer yes to this question.

	No
	Yes

No → If no, skip the rest of this question; go to [question 5.8](#)

Yes → If yes, answer all of the questions below.

a. Describe the PHI you will access or obtain, and the reason for obtaining it. *Be specific.*

We will obtain the health information that is in the clinical charts at the study sites where participants are enrolled that is relevant to PrEP follow-up. All participants will sign a HIPAA Authorization and an ROI at study entry. This data will include appointment dates, behavioral eligibility for PrEP, any reported side effects from PrEP, prescription orders and refills, reported PrEP adherence, any discontinuation of PrEP and reason, and other information that may be recorded regarding their PrEP use and follow-up.

b. Is any of the PHI located in Washington State?

	No
	Yes

c. Describe how you will access or obtain the PHI. *Be specific.*

At study entry, all participants will sign a HIPAA Authorization and an ROI between the clinic site and the UW study team to share PrEP-related clinical records.

d. For which PHI will you obtain HIPAA authorization from the subjects by having them sign a HIPAA Authorization form, before obtaining and using the PHI?

We will ask participants to authorize us to access their PrEP-related medical records using both a HIPAA Authorization and an ROI prior to obtaining any PHI.

Confirm by checking the box that you will use the UW Medicine [HIPAA Authorization](#) form maintained on the HSD website if you will access, obtain, use, or disclose UW Medicine PHI.

	Confirmed
-------------------------------------	-----------

e. For which PHI will you NOT obtain HIPAA authorization from the subjects?

None.

Provide the following assurances by checking the boxes.

The PHI will not be reused or disclosed to any other person or entity, except as required by law, for authorized oversight of the research study, or for other research for which the use or disclosure of PHI would be permitted.

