b. Describe what will be shared, including whether direct identifiers will be shared and (for specimens) what data will be released with the specimens.

c. Who will oversee and/or manage the sharing?

d. Describe the possible future uses, including limitations or restrictions (if any) on future uses or users. As stated above, consider the broadest possible uses.

Examples: data will be used only for cardiovascular research; data will not be used for research on population origins.

e. Consent. Will you obtain consent now from subjects for the banking and/or future sharing?

No

Yes

→ If yes, be sure to include the information about this consent process in the consent form (if there is one) and in your answers to the consent questions in [Section 8](#).

f. Withdrawal. Will subjects be able to withdraw their data/specimens from banking or sharing?

No

Yes

→ If yes, describe how, and whether there are any limitations on withdrawal.

Example: data can be withdrawn from the repository but cannot be retrieved after they are released.

g. Agreements for sharing or release. Confirm by checking the box that you will comply with UW (and, if applicable, UW Medicine) policies that require a formal agreement between you and the recipient for release of data or specimens to individuals or entities other than federal databases.

Confirmed

5.11 Communication with subjects during the study. Describe the types of communication (if any) you will have with already-enrolled subjects during the study. Provide a description instead of the actual materials themselves.

Examples: email, texts, phone, or letter reminders about appointments or about returning study materials such as a questionnaire; requests to confirm contact information.

For all participants we will send them a link to the survey at baseline, month 3 and month 6 and reminders if they do not complete it. For the participants assigned to the standard of care group, we will not have additional contact. For participants in the peer navigation group, the peer navigator will have varied communication (in-person, email, phone, text) in response to the requests of the participant. Once participants have completed their 6-month survey, or if they discontinue the study early, we will contact them and ask if they would like to participate in an end-of-study interview.

New activities for all MSM/TGP participants and PrEP providers:

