d. Influence. Does your research involve any subject groups that might find it difficult to say "no" to your research because of the setting or their relationship with you, even if you don't pressure them to participate?

Examples: Student participants being recruited into their teacher's research; patients being recruited into their healthcare provider's research, study team members who are participants; outpatients recruited from an outpatient surgery waiting room just prior to their surgery.

	No
	Yes

→ If yes, describe what you will do, for each of these subject groups, to reduce any effect of the setting or relationship on their decision.

Examples: a study coordinator will obtain consent instead of the subjects' physician; the researcher will not know which subjects agreed to participate; subjects will have two days to decide after hearing about the study.

The lead researcher is also the prescribing physician at the Gay City Health Project. If she has a potential client who is eligible to participate, she will inform them of the study and emphasize that they can continue to get PrEP at Gay City without participating if that is their preference. The Gay City PrEP clinic is not a primary care clinic, but instead is a safety net clinic that follows people who initiate PrEP until they can be linked to a primary care provider for continued use (typically up to a few months) and assists with this linkage. So the PI is not the primary care provider for the Gay City PrEP clients. All clients who decide not to initiate PrEP are provided information on other locations to get it if they so choose to in the future.

e. Ongoing process. For research that involves multiple or continued interaction with subjects over time, describe the opportunities (if any) you will give subjects to ask questions or to change their minds about participating.

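### Transfer to outside primary care before month 6 is the normal course at Gay City, but the release signed at entry covers only the enrolling clinic, so chart and refill data after transfer are at risk

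*Protocol*

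**What the plan says.** Protocol 8.2.d explains that the Gay City PrEP clinic is a safety-net service, not a primary care clinic. It "follows people who initiate PrEP until they can be linked to a primary care provider for continued use (typically up to a few months") and helps with that linkage. Section 5.1 sets study visits at baseline and months 1, 3 and 6.

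Section 5.7.c says that at entry participants "sign a HIPAA Authorization and an ROI between the clinic site and the UW study team to share PrEP-related clinical records". Section 5.7.a describes the data as "health information that is in the clinical charts at the study sites where participants are enrolled", limited to what bears on PrEP follow-up: appointments, prescriptions and refills, reported adherence, and any discontinuation with its reason. Section 5.3 adds: "We will also obtain PrEP pharmacy refill data as available".

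Section 5.1 deals with a participant who decides to leave a study clinic and gets PrEP somewhere else. That person is asked to take the remaining surveys and to "complete an ROI between their new clinic and the study site where they enrolled". Those assigned to an intervention are asked to continue it at the new provider.

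Section 5.11 describes survey links and reminders for everyone, and then states: "For the participants assigned to the standard of care group, we will not have additional contact". The navigation arm has varied, ongoing contact with the peer.

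**The concern.** Section 5.1 handles a change of PrEP provider as an occasional event that the participant starts. Section 8.2.d makes it the clinic's ordinary course at one of the two named sites, on a time scale shorter than follow-up. The record access in 5.7 suits the first picture and not the second. Once a Gay City participant has been linked elsewhere, later charts and refills depend on a second release that is requested after the move and is worded as an arrangement between two clinics.

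At stake are the PrEP follow-up data after transfer: prescriptions, refills, clinic-reported adherence and discontinuation. Section 1.8 gives persistence and adherence as the problem behind the study, so these data matter even in a pilot. If the second release is completed less often in one arm, completeness of records would differ by arm for reasons unrelated to PrEP use. The navigation arm has someone in regular contact who may learn of a transfer and prompt the paperwork; the control arm does not.

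**Working it through.** The protocol states no transfer rate, release-completion rate or expected loss, so there is no figure to reproduce. The check has two parts.

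**Sections side by side**

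- *Expected path.* 8.2.d: linkage out of Gay City, typically within a few months. 5.1: follow-up to month 6. Many Gay City participants can therefore be expected to move during the study.
- *Trigger.* 5.1: the participant's decision. 8.2.d: the clinic's routine. The two need reconciling.
- *Parties.* Entry release (5.7.c): enrolling clinic and UW. Later release (5.1): new clinic and enrolling site, with UW not named.
- *Contact needed.* 5.1 asks movers in either arm for the later release. 5.11 describes no further contact with controls beyond surveys and, at the end, the interview invitation. These also need reconciling.

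**Illustration, on assumptions only**

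Arm size is up to 20 (2.7 and 5.1). The other inputs are assumed:

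- g, share enrolled at Gay City: 0.33 to 0.80. Section 3.1 gives no enrolment share and opens the study to other King County providers.
- t, share of those handed off before month 6: 0.5 to 0.9.
- u, share of movers without a completed second release.
- True persistence of 50% in both arms.

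Participants per arm without later chart data = 20 × g × t × u.

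Spurious difference if every missing record is counted as stopped = 0.5 × g × t × (u in controls − u in navigation).

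| u, controls / navigation | Low end (g = 0.33, t = 0.5) | High end (g = 0.80, t = 0.9) |
|---|---|---|
| 0.30 / 0.30 | 20 × 0.33 × 0.5 × 0.30 = 1.0 in each arm; difference 0 | 20 × 0.80 × 0.9 × 0.30 = 4.3 in each arm; difference 0 |
| 0.50 / 0.20 | 1.7 v 0.7; 0.5 × 0.165 × 0.30 = 2.5 points | 7.2 v 2.9; 0.5 × 0.72 × 0.30 = 10.8 points |
| 0.60 / 0.10 | 2.0 v 0.3; 0.5 × 0.165 × 0.50 = 4.1 points | 8.6 v 1.4; 0.5 × 0.72 × 0.50 = 18.0 points |

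With equal completion there is no difference between arms, and the cost is precision. At 50% in both arms, the 95% half-width for a difference is 1.96 × √(0.5/20) = 31 points with 20 per arm and 1.96 × √(0.5/15) = 36 points with 15. If completion were better in controls, the sign of the spurious difference would reverse.

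**The case against.** The strongest reply is that little is actually lost.

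- **Other data continue.** 5.1 asks movers to take the remaining surveys, and surveys go to both arms. Dried blood spots are scheduled for everyone at months 1, 3 and 6. This stands and offsets part of the loss. The offset is partial: surveys are self-report, and 3.1 ties blood-spot collection to the site while the 5.1 text on movers does not mention it.
- **The two releases can work as a chain.** New-clinic records go to the enrolling site, and the entry release lets UW have PrEP-related records from there. This is possible, but it relies on a clinic that no longer follows the patient to collect and file those records.
- **5.11 need not bar the request.** A reader might infer that controls cannot be asked for the second release. The documents do not support that: 5.1 makes the request of any mover, and 8.2.e says clinic staff stay in communication during PrEP follow-up. The two sections fit badly, but neither prohibits the request.
- **A transferred control need not look like one who stopped.** That inference is tempting, but Gay City assists the linkage, and 5.7.a includes discontinuation and its reason among the chart data. What may be missing is detail after the transfer.
- **The forms are not shown.** It cannot be said that they leave out pharmacies. The protocol says only that refill data are obtained where available.
- **The stakes are modest.** Section 1.5 aims at acceptability and feasibility, and persistence is not a named outcome. This stands.

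**Conclusion.** The point holds as a risk of missing post-transfer chart and refill data among Gay City participants before month 6. It rests on the text of 5.1, 5.7 and 8.2.d. The hand-off is documented for Gay City only, and that site's share of enrolment is not given.

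A reader might go further and conclude that persistence data will be lost, and lost more often in controls, so that navigation appears to help. The unequal contact makes greater loss in controls plausible, but the documents establish neither the size nor the direction of any imbalance. The illustrative differences of 2.5 to 18 points depend on assumed transfer and release rates and on counting every untraced participant as stopped, a rule the protocol does not state. They become zero if release completion is equal between arms. The effect falls on secondary PrEP follow-up data in a feasibility pilot. The change is still worth making, because the path is expected and prevention is cheap.

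**What to change.** At entry, have participants in both arms sign one release and HIPAA authorization with UW as recipient, covering the enrolling clinic, any later PrEP prescriber and dispensing pharmacies through month 6. Keep a later release as a fallback, requested by the research coordinator in the same way in both arms, and amend 5.11 so that it allows for this request. Reword 5.1 so that it covers routine linkage from Gay City as well as a participant's own choice to go elsewhere.

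Under the assumptions above, if everyone signs at entry, loss due to an unsigned second release falls to 0 of 20 in each arm; loss from other causes is unchanged. The cost is a revised form, a short amendment and possibly a few participants who decline the broader release. No new visits, staff or participants are needed.
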